1 LIST OF ABBREVIATIONS

ADE	Adverse Device Effect
AE	Adverse Event
AF	Atrial Fibrillation
AIMD	Active Implantable Medical Device (Directive 90/385/EEC)
ASADE	Anticipated Serious Adverse Device Effect
AU	Australia
bpm	Beats Per Minute
CA	Competent Authority
CCR	Center for Clinical Research; BIOTRONIK SE & CO. KG study department
CDMS	Clinical Datamanagement System
CE	CE mark, a stylized "CE" (Conformité Européenne) placed on products to signify conformance with European Union regulations
CEC	Clinical Event Committee
CFR	Code of Federal Regulations der USA (www.gpoaccess.gov/cfr)
CI	Coordinating Investigator
CIP	Clinical Investigation Plan
CIR	Clinical Investigation Report
CRA	Clinical Research Associate
CRF	Case Report Form
CRT	Cardiac Resynchronization Therapy
DAL	Device Accountability Log
DD	Device Deficiency
EC	Ethics Committee
ECG	Electrocardiogram
eCRF	electronic Case Report Form
EDC	Electronic Data Capture
EMI	Electromagnetic Interference
EP	Electrophysiology
ESC	European Society of Cardiology
EU	European Union
FDA	US Food and Drug Administration (www.fda.gov)
FIT	Fast Insertion Tool
FPI	First Patient In
FU	Follow-up visit
GDPR	General Data Protection Regulation
HIPAA	Health Insurance Portability and Accountability Act
HM	Home Monitorig

BIOTRONIK SE & Co.KG // BIO|MASTER.BIOMONITOR III

HMSC	Home Monitorig Service Center
HVR	High ventricular rate
Hz	Hertz
ICD	Implantable Cardioverter Defibrillator
ICF	Informed Consent Form
ICH	International Conference on Harmonisation of Technical Requirements for Registration of Pharmaceuticals for Human Use (www.ich.org)
ICM	Implantable cardiac monitor
ICS	Implant Control System (e.g. BIOTRONIK's ICS 3000)
ID	Identification Number
IFU	Instructions For Use (user manual)
iMedNet	Web-based electronic data entry (EDC) system for clinical trials provided by MedNet Solutions Inc.
IIRB	Institutional Review Board
ISO14155	International Organization for Standardization, norm no. 14155
LOC	Loss of concousness
LPI	Last Patient In
LPO	Last Patient Out
MEDDEV	Collection of guidelines of the European Commission for conformity assessment of medical devices
MedNet	Supplier of Clinical Trial Software (MedNet Solutions, Inc. www.mednetstudy.com)
MR	Magnetic Resonance
MRI	Magnetic Resonance Imaging
PAC	Premature Atrial Contraction
PDF	Portable Document Format (www.adobe.com)
PI	Principal Investigator
PMCF	Post Market Clinical Follow-up
PPV	Positive predictive value
PVC	Premature ventricular contraction
QRS	Electrical complex on an ECG related to the depolarization of the ventricles
SaaS	Software as a Service
SADE	Serious Adverse Device Effect
SAE	Serious Adverse Event
SAP	Statistical Analysis Plan
SAS	Statistics and Analysis Software produced by SAS Institute Inc. (www.sas.com)
SDS	Source Data Sheet
sECG	subcutaneous echocardiogram
SOP	Standard Operating Procedure
SRD	Sudden rate drop

BIOTRONIK SE & Co.KG // BIO|MASTER.BIOMONITOR III

TGA	Therapeutic Goods Administration
UBD	Used before date
UMTS	Universal Mobile Telecommunications System
US	United States
USA	United States of America
USADE	Unanticipated Serious Adverse Device Effect
USB	Universal Serial Bus
VER	Validation / Verification Results
VES	Ventricular Extrasystole
Vs	Ventricular Sensing Events
ZIP	File compression format

2 SYNOPSIS

Title	BIO MASTER.BIOMONITOR III
Patient population	The patient population consists of patients in whom long-term cardiac rhythm monitoring is required for diagnostic purposes.
Design	Multicenter, international, prospective, non-randomized, non-controlled, open-label
Investigational device(s)	BIOMONITOR III insertable cardiac monitor, including incision and insertion tool (FIT OneStep)
Objectives	This study is a post-market clinical follow-up (PMCF) study to identify and evaluate residual risks associated with the use of the BIOMONITOR III that are discovered or remain even after risk analysis, risk mitigation and successful conformity assessment. Furthermore, this study will also provide additional data as required by regulatory authorities outside of the CE-region.
Primary endpoint	SADE-free rate related to BIOMONITOR III including incision and insertion tool set until 3-month follow-up
Secondary endpoint(s)	
 • R-wave amplitude at 1st follow-up and 3-month follow-up • Noise burden at 1st follow-up and 3-month follow-up • P-wave visibility at 1st follow-up and 3-month and 12-month follow-up • SADE-free rate related to BIOMONITOR III from insertion until 12-month follow-up
Inclusion criteria	
 • Patient is at high risk of developing a clinically important cardiac arrhythmia; or Patient is undergoing investigation for symptoms such as palpitations, pre-syncope or syncope, that are suggestive of an underlying cardiac arrhythmia; or Patient is undergoing investigation for the detection of atrial fibrillation following cryptogenic stroke; or Patient is planned for AF ablative procedure or

has already undergone an AF ablative procedure.

- Patient is able to understand the nature of the study and able to provide written informed consent.
- Patient is willing and able to perform all follow-up visits at the investigational site.
- Patient is willing and able to use the CardioMessenger and accepts the BIOTRONIK Home Monitoring concept.

Exclusion criteria

- Patient is implanted with an ICD or pacemaker.
- Patient is pregnant or breast-feeding.
- Patient is less than 18 years old.
- Patient's life-expectancy is less than 12 months.
- Patient is participating in another interventional clinical investigation.

Study duration Sep 2019 – Aug 2021

Sample size 157

Investigational sites Up to 30

Number of follow-ups per patient 4 (including insertion)

Follow-up scheme Enrollment – Insertion – 1st follow-up – 48-hour Holter ECG recording* – 3-month follow-up – 12-month follow-up

* It is recommended to start Holter recording immediately after the completion of the 1st follow-up procedure (see 9.6).

Coordinating Investigator [REDACTED]

Boards (if applicable) None

Sponsor BIOTRONIK SE & Co.KG
[name]
[name]

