7.2.2 Secondary endpoints

The following 4 secondary endpoints are defined for the study.

R-wave amplitude

The **secondary endpoint 1** evaluates the R-wave amplitude at the 1st follow-up and at 3-month follow-up by measuring both, the lowest and the highest amplitude value via the programmer.

Noise burden

The **secondary endpoint 2** evaluates the noise burden at the 1st follow-up and at 3-month follow-up by retrieving the percentage of noise via the programmer.

Assessment of P-wave visibility

The **secondary endpoint 3** evaluates the P-wave visibility at 1st, 3- and 12-month follow-up. The investigator will evaluate whether P-waves can be recognized in the stored sECGs showing sinus rhythm. The number of heart cycles and observed P-waves which can undoubtedly be identified in ECGs will be assessed by the investigator.

SADE-free rate until the 12-month follow-up

The **secondary endpoint 4** is the SADE-free rate related to the BIOMONITOR III 12 months after insertion.

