8.3.5.4 Drop-out according to protocol

The investigator shall exclude a patient due to the following reasons and after all adverse events have been reported and the corresponding eCRFs have been thoroughly completed:

- Patient with no insertion attempt of the BIOMONITOR III within 4 weeks of enrollment
- Patients in whom the insertion fails and no new attempt is planned are terminated after complete reporting of the insertion attempt and all adverse events connected to the failed insertion.
- Patients in whom the BIOMONITOR III was replaced/explanted/deactivated are terminated after complete reporting of the explantation and all adverse events connected to the explantation.

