8.3.6 Point of enrollment and study termination

The date of enrollment is the date of the informed consent form. Study related procedures, documentation and collection/following of adverse events will start from this time on.

The point of study termination is defined as date of 12-month follow-up for patients with regular study termination.

In case of premature study termination the following rules apply:

- If patients are permanently unable to attend required follow-ups, e.g. if they move away from the investigational site the date of study termination should be the date of last contact of the study team (e.g. investigator or study nurse) with the patient.
- If patient is lost to follow-up, the date of termination shall be the last day, from which the investigator can assume that possible adverse events – had any occurred – would have been reported. In most cases, this would be the date of the last follow-up contact.
- In case of withdrawal of a patient's consent, the date of study termination should be the date of withdrawal of consent.
- If the investigational device could not successfully be inserted, the date of study termination should be the date of the last unsuccessful insertion attempt.
- If the BIOMONITOR III is replaced/explanted/deactivated (e.g. due to subsequent therapies with pacemaker or ICD etc.), the date of termination is the date of explantation.
- In case of patient death, the date of study termination should be the date of death.
- In case the patient terminated prior to study specific procedures because a violation of an inclusion/exclusion criterion was discovered the date when the violation was discovered shall be the date of termination.

Study related procedures and documentation should end at the day of study termination for the respective patient. However, all Serious Adverse Device Effects will be followed for up to 4 weeks after study termination of the respective patient.

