## 5. General Statistical Procedures

### 5.1. Descriptive analyses

CIP chapter ...

...

For continuous variables descriptive statistics (mean, standard deviation, minimum, 1. quartile, median, 3. quartile and maximum) will be calculated. For nominal variables absolute numbers and relative frequencies based on the non-missing data will be determined. Ordinal data are described by the 1st quartile, median, and 3rd quartile as well as the absolute numbers and relative frequencies based on the non-missing data of each category.

For illustration, see the following standard tables with and without subgroup analyses based on dummy data.

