## 5.4. Missing Data

*CIP chapter 11.11 Handling of missing, unused and spurious data*

*Missing or spurious data will not be imputed and not be used for analysis. More details will be specified in the SAP.*

Missing data will not be imputed. Free text will be used to clarify other data. Spurious data will be clarified via the query management, i.e. corrected after approval of an investigator. Remaining outliers will be identified during the review of the data before data base closure and will be reported in the Blind Review Report. In case of a clear evidence of a measurement error, the Statistical Analysis Plan will be updated in order to avoid any bias. Spurious data, which were not clarified by the query process before database closure, will be indicated. If appropriate, analyses will be performed both with /without such data.

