### 12.2. Variables

| Data file, identifier patient_display_id_full | Notes | Variable name | Variable label | Variable level | Nominal values |
|---|-------|---------------|----------------|----------------|----------------|
| follow_up_1st                                 |       | DUNSE         | Noise [%]      | Scale          |                |
| follow_up_3months                             |       | DUNSE         | Noise [%]      | Scale          |                |
| follow_up_12months                            |       | DUNSE         | Noise [%]      | Scale          |                |

Moreover, the proportions of patients with "Noise smaller 5% vs. at least 5%" will be reported for the 1 month FU, 3 months FU and 12 months FU separately and in total (all FU together). Therefore the variable "DUNSE" will be recoded accordingly.

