15.2.5 Data of interests derived from the CRFs "Deactivation/Explantation" only

This includes the following data of interest:

- Explantation data of BIOMONITOR III
- Diagnosis and further treatment
- Additional implantation of BIOMONITOR III

In addition to the descriptive reporting of the parameters related to diagnosis and further treatment, a case-by-case listing shall be provided for all patients with a deactivation or explantation. This listing shall contain the following variables:

Baseline CRF:

|          |   |
|----------|---|
| CEINDICM | Primary type of ICM indication                        |
| COINDICM | Specification of other primary type of ICM indication |

Deactivation/Explantation CRF:

|          |   |
|----------|---|
| DXEXREA  | Reason for explantation/deactivation                    |
| PRDGNDT  | Date of diagnosis                                       |
| DUBMDGN  | Did the BIOMONITOR III contribute to this diagnosis?    |
| DUBMDGNA | How did the BIOMONITOR III contribute to the diagnosis? |
| CVARTYP  | Specify arrhythmia type detected                        |
| QSFTRT01 | Ablation procedure                                      |
| QSABPR   | Specify the ablation procedure                          |
| QSFTRT02 | Medication  |
| QSCM01   | Anticoagulation   |
| QSCM02   | Antiarrhythmics   |
| QSCMOTH  | Other   |
| QSFTRT03 | ICD implantation  |
| QSFTRT04 | Pacemaker implantation                                  |
| QSFTRTOT | Other   |
| QSBMU    | Further use of the BIOMONITOR III                       |

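### A device given up for poor sensing leaves the later R-wave and noise summaries, which tilts them in the device's favour by an unknown and possibly small amount

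*Protocol*

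**What the plan says.** Protocol 7.2.2 states that secondary endpoint 1 "evaluates the R-wave amplitude at the 1st follow-up and at 3-month follow-up". Endpoint 2 is read at the same two visits; the synopsis has it as "Noise burden at 1st follow-up and 3-month follow-up". The 12-month values of both are additions in the variable tables of SAP 11.2 and 12.2. SAP 12.2 also splits noise at 5% and says that the proportions "will be reported for the 1 month FU, 3 months FU and 12 months FU separately and in total (all FU together").

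On removal, protocol 8.3.5.4 says: "Patients in whom the BIOMONITOR III was replaced/explanted/deactivated are terminated after complete reporting of the explantation". Under 8.3.6, "the date of termination is the date of explantation", and study procedures end on that day apart from a short follow-up of SADEs. Protocol 9.7 defines deactivation as a permanent decision to stop using the device's information and does not restrict the reason.

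On missing values, SAP 5.4 says "Missing data will not be imputed", and protocol 11.11 adds that missing data are not used. SAP 5.1 sets the denominator: "For nominal variables absolute numbers and relative frequencies based on the non-missing data will be determined". SAP 11 and 12 name the full analysis set and exclude no data. Neither has a rule for a device that was given up. SAP 15.2.5 lists every explantation or deactivation with "Reason for explantation/deactivation" (DXEXREA), but does not connect this to endpoints 1 and 2.

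**The concern.** Protocol 7.1.2 makes verification of sensing performance a secondary objective. Protocol 5.3 expects somewhat smaller R-waves because of the shorter vector and leaves open an effect on detection. Protocol 18.7 lists oversensing and undersensing among the anticipated events, with a frequency that cannot be assessed.

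A device abandoned because its signal is unusable is an informative case for that objective. Under the plan it contributes nothing to any later R-wave or noise summary, and it contributes fewer visits to the pooled noise proportion. The full-analysis-set label does not prevent this, because membership of the set does not supply a value.

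The effect runs one way: the share with noise of at least 5% comes out too low and the R-wave distribution too high. A series of visits could also look stable or improving because failures have left. The primary endpoint is protected against informative exit: patients with an event stay in numerator and denominator without a 3-month visit, and protocol 11.12 removes early event-free leavers so as not to overstate the rate. The sensing endpoints have no comparable provision.

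**Working it through.** **The plan's own figure.** The plan states no sample size, precision target or expected value for R-wave or noise. Its only sample-size calculation (protocol 11.2) concerns the primary endpoint. With 90% against 97%, one-sided alpha 0.025 and power 90%, the normal approximation gives 132.8, so 133. The exact binomial test at n = 141 has power 93.7%. Then 133/0.9 gives 148 and 141/0.9 gives 157. All four stated figures reproduce, and the present point changes none of them.

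**Mechanism.**
1. Removal or deactivation for any reason leads to termination on that day (protocol 8.3.5.4, 8.3.6).
2. There is then no noise or R-wave value at later visits.
3. Missing values are neither imputed nor used (protocol 11.11, SAP 5.4).
4. Percentages are based on non-missing data (SAP 5.1).
5. It follows that a device removed for poor sensing leaves both numerator and denominator at each later visit.

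**Size, noise at 3 months, adding removals back.** All inputs are illustrative except n = 141, which is the evaluable number in protocol 11.2. Let x be the number of measured patients with noise of at least 5%, and k the number of further patients whose device was given up for poor sensing before the visit. The planned figure is x/141; counting removals as failures gives (x + k)/(141 + k).

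| Assumed x | Planned | k = 1 | k = 3 | k = 6 |
|---|---|---|---|---|
| 14 | 14/141 = 9.9% | 15/142 = 10.6% | 17/144 = 11.8% | 20/147 = 13.6% |
| 7 | 7/141 = 5.0% | 8/142 = 5.6% | 10/144 = 6.9% | 13/147 = 8.8% |

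**Size, noise, from the full cohort downwards.** Take 157 inserted devices, assume a true number b with noise of at least 5%, and assume that all k removed devices belong to that group. The reported share is (b − k)/(157 − k).

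| Assumed b | True share | k = 2 | k = 5 | k = 8 |
|---|---|---|---|---|
| 16 | 10.2% | 14/155 = 9.0% | 11/152 = 7.2% | 8/149 = 5.4% |
| 31 | 19.7% | 29/155 = 18.7% | 26/152 = 17.1% | 23/149 = 15.4% |

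Two removals move the figure by about 1 percentage point; eight move it by 4 to 5 points.

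**Size, R-wave.** Assume a normal distribution with SD 0.2 to 0.4 mV and removal of exactly the lowest values, which is the worst case. With s = k/157, the mean rises by SD × φ(z_s)/(1 − s), where z_s is the standard normal quantile at s and φ its density. This gives 0.007 to 0.013 mV for k = 2 and 0.022 to 0.044 mV for k = 8. For scale, the predecessor's mean was 0.75 mV (protocol 5.2.4).

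**The case against.** The strongest case against has four parts.

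- **No evidence of frequency.** No passage reports a device removed for poor sensing. The predecessor study describes two explantations, both for risk of erosion (protocol 5.2.4), and protocol 8.2.4 calls device exchange unlikely. With 157 − 141 = 16 drop-outs allowed for, k = 6 would take 6/16 = 38% of them. Even then the adjusted figures lie inside the exact 95% intervals of the planned ones: 5.5% to 16.1% for 14/141 and 2.0% to 10.0% for 7/141.
- **Disclosure exists.** SAP 8 lists date and reason for every premature termination, the standard tables show the non-missing count, and SAP 15.2.5 gives a case listing with the reason for removal.
- **The endpoints are descriptive.** They carry no hypothesis (SAP 5.2) and are exploratory (SAP 5.3); protocol 11.5 rests pass/fail on the primary hypothesis alone.
- **Low amplitude or undersensing is not measured noise of at least 5%.** Scoring such a patient as noisy assigns a value that was never recorded.

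The first three limit the importance but leave the mechanism intact. Lying inside a sampling interval does not excuse a one-directional bias, and the listings leave the reader to rebuild the adjusted figure by hand. The fourth stands in full, and it is why the added proportion must be labelled a composite and set beside the observed-case result.

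A reader might infer that the 3- and 12-month results describe only devices good enough to keep in use. The documents do not support that. Poor but tolerated devices stay in, as do reprogrammed ones (protocol 4.7.1.1 offers five sensing programs, and 9.4 allows adjustment at each follow-up). Others leave for unrelated reasons, such as later pacemaker or ICD therapy (8.3.6).

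**Conclusion.** The point holds as a cheap improvement to the SAP. Any device given up for poor sensing or noise leaves the 3-month summaries of protocol endpoints 1 and 2, the 12-month summaries that the SAP adds, and the pooled noise proportion. The resulting bias favours the device. The 1st follow-up, at 10 days to 4 weeks, is largely untouched, since only a removal before that visit matters.

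The size is unknown and may be small, especially by 3 months. Every baseline and every k above is an assumption. Within those ranges the noise share moves by less than 1 point for one removal and by roughly 4 to 5 points for six to eight. A larger effect at 12 months is plausible because there is more time for removals, but the documents give no figure for it. The primary pass/fail result does not change.

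**What to change.** Leave the observed-case noise and R-wave summaries as they are, and add the following before database closure, while protocol 11.8 still allows SAP updates.

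- **SAP 12.2:** a supplementary proportion per visit, labelled as a composite: noise smaller than 5% and device not given up for inadequate sensing or noise. A patient whose device was replaced, explanted or deactivated for that reason counts as a failure at every later visit. The reason comes from DXEXREA, clarified by free text as SAP 5.4 permits, because the answer categories of DXEXREA are not shown.
- **SAP 11.3:** beside each visit's R-wave summary, the number of such patients and their last recorded R-wave value.
- **Both sections:** removals for a diagnosis, other device therapy, patient wish or end of use stay missing.

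The cost is SAP wording, one derived variable and a little more analysis work. No new visits, patients or sample-size change are needed, provided that the recorded reason and free text identify poor sensing. The reported figure may become slightly less favourable.

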3 INTRODUCTION

Implantable Cardiac Monitors (ICMs) are devices which allow cardiac rhythm monitoring for a long time-period. The principal function of these devices is to establish long term continuous cardiac rhythm monitoring to achieve a close correlation between symptoms and arrhythmia.

Typically, ICMs have a retrospective loop memory, which continuously records the most recent minutes of a patient's subcutaneous electrocardiogram (sECG). Data saving of an electrocardiogram can be triggered by three different mechanisms. Most current devices have a patient-activation function, which allows the patient to activate ECG storage (with the help of a user-trigger-device) following a symptomatic episode. Additionally, an auto-detection function allows the capture of arrhythmic events without relying on patient compliance or the perception of symptoms. Finally, a sECG can be captured via a pre-programmed periodic recording.

The most common application of ICMs is the diagnosis of unexplained recurrent syncope. The availability of Implantable Cardiac Monitors has extended the diagnostic opportunities beyond conventional long-term ECGs and the 12-channel ECG. The clinical domain of event recording consists of ECG recording in the case of recurrent syncope of unclear etiology as well as the evaluation of unclear palpitations. Especially with regard to syncope diagnostics, long-term surface ECG achieved a diagnosis in only 4% of patients with syncope even when extended to a duration of 72 hours¹. It is in this context that ICMs have been utilized and have fast become an important tool in the early stage of the diagnostic approach. ICM insertion is recommended by the current ESC guidelines for the management of patients with syncope². A further application of ICMs is in the detection and management of atrial fibrillation. The detection of AF is crucial in patient populations at high thromboembolic risk and ICMs have been shown to accelerate the detection of paroxysmal AF in this group³. This finding has important clinical repercussions. In addition, undiagnosed 'silent AF' is often suspected to be the cause of cryptogenic strokes⁴⁻¹². In patients who have already had a stroke, identification of AF as the cause is critical to initiating proper therapy^{13,14}. Early recognition of AF is critical for stroke prevention¹⁵.

Furthermore, ECG monitoring is crucial in assessing the efficacy of rhythm control therapies in patients with established AF. Since AF is often unsymptomatic and the distribution and duration of AF recurrences stochastic, ICMs can objectify the amount of AF. The capabilities of these devices open a wide field of diagnostic potential¹⁶. The experiences with the second generation of BIOTRONIK's ICM - BioMonitor 2 - since its market introduction in 2015 established the efficacy of its arrhythmia detection software. These well-established software algorithms have now been adopted in the smaller hardware of the BIOMONITOR III.

Like its predecessor ICMs, it is equipped with the Home Monitoring feature, which supports the daily transmission of device stored data including recordings of the subcutaneous ECG triggered by automatic detection, periodic recording or patient activation.

The third generation ICM, BIOMONITOR III, is the subject of this clinical investigation. The most important improvement over its predecessor is its miniaturization while retaining a particularly long sensing vector. This feature will provide large R-wave amplitudes and due to fractal coating of the electrodes and a lossless ECG data compression algorithm improve P-wave visibility, yielding a higher diagnostic value. Miniaturization of the device will improve wearing comfort and allows for an easier, injection-like insertion procedure.

Aims of the study

It is known that the distance between the electrodes of the ICM correlates approximately linearly with the sensing amplitude, supporting the development of longer devices for better signal quality¹⁷. Nevertheless, the patient comfort is increased with reduced device size. Thus, BIOTRONIK's goal for the third generation of ICM was to develop a device with a substantially reduced device volume than its predecessor BioMonitor 2. With the BIOMONITOR III, the two conflicting goals – reduced device size while maintaining a long sensing vector - were realized with the combination of a rigid and a flexible part of the device body (rigid coated housing-flex lead concept) and the fractal coating of the electrodes (lead tip and distal end of the housing) which is intended to improve signal quality.

Furthermore, the insertion procedure was improved: the new device is inserted via a novel, single insertion tool, onto which it is pre-mounted and therefore insertion has now become a simplified procedure.

This study is a post-market clinical follow-up (PMCF) study to identify and evaluate residual risks associated with the use of the BIOMONITOR III that are discovered or remain even after risk analysis, risk mitigation and successful conformity assessment. Furthermore, this study will also provide additional data as required by regulatory authorities outside of the CE-region.

